**Table 3. Study Objectives and Endpoints (Cohorts B1 and B2)**

including but not limited to biomarkers related to anti-tumor immune response or target modulation (Cohorts B1 and B2).	
---	--

### 2.2.1. Primary estimand (Cohort A only)

Primary Estimand (EFS for Arm A vs Arm C): treatment effect, estimated based on data from all randomized participants, of Arm A on EFS compared to Arm C from randomization to the earliest of recurrence of high-grade disease, progression of disease, persistence of CIS, or death regardless of tolerability, duration of study treatment, or initiation of subsequent anti-cancer therapy. The date of the event (event as defined in Table 10) is the date of disease assessment documenting recurrence of high-grade disease, progression of disease, persistence of CIS (applicable only to participants with CIS at randomization), or death, whichever occurs earlier. The date of persistence of CIS is the earliest date when persistence of CIS is observed, if CR is not observed after re-induction.

- Variable: EFS defined as the time from randomization until recurrence of high-grade disease, progression of disease, persistence of CIS or death due to any cause, whichever occurs first.
- Censoring: see Table 11.
- Population-level summary measure: hazard ratio for EFS including all randomized participants.

### 2.2.2. Secondary estimands (Cohort A only)

Key Secondary Estimand (EFS for Arm B vs Arm C): treatment effect, estimated based on data from all randomized participants, of Arm B on EFS compared to Arm C from randomization to the earliest of recurrence of high-grade disease, progression of disease, persistence of CIS, or death regardless of tolerability, duration of study treatment, or initiation of subsequent anti-cancer therapy. The date of the event (event as defined in Table 10) is the date of disease assessment documenting recurrence of high-grade disease, progression of disease, persistence of CIS (applicable only to participants with CIS at randomization), or death, whichever occurs earlier. The date of persistence of CIS is the earliest date when persistence of CIS is observed, if CR is not observed after re-induction.

- Variable: EFS defined as the time from randomization until recurrence of high-grade disease, progression of disease, persistence of CIS or death due to any cause, whichever occurs first.
- Censoring: see Table 11.
- Population-level summary measure: hazard ratio for EFS including all randomized participants.

Key Secondary Estimand (OS): treatment effect, estimated based on data from all randomized participants, of each experimental arm (Arm A and Arm B) on OS compared to

Arm C regardless of tolerability, duration of study treatment, initiation of subsequent anti-cancer therapy or participant's request to discontinue study procedures.

- Variable: OS
- Censoring: data for participants not known to have died are censored at the time of last contact.
- Population-level summary measure: hazard ratio for OS, including all randomized participants.

### 2.2.3. Additional estimands (Cohort A only)

Supportive Estimand 1 (EFS): treatment effect, estimated based on data from all randomized participants, of each experimental arm (Arm A and Arm B) on EFS compared to Arm C from randomization to the earliest of recurrence of high-grade disease, progression of disease, persistence of CIS, or death, regardless of tolerability, duration of study treatment or initiation of subsequent anti-cancer therapy. The date of the event (event as defined in Table 10) is the date of disease assessment documenting recurrence of high-grade disease, progression of disease, date of randomization for participants with persistent CIS (applicable only to participants with CIS at randomization), or death, whichever occurs earlier.

- Variable: EFS defined as the time from randomization until recurrence of high-grade disease, progression of disease, persistence of CIS, or death due to any cause, whichever occurs first.
- Censoring: see Table 11
- Population-level summary measure: hazard ratio for EFS including all randomized participants.

Supportive Estimand 2 (EFS): treatment effect of each experimental arm (Arm A and Arm B) on EFS compared to Arm C from randomization to the earliest of recurrence of high-grade disease, progression of disease, persistence of CIS, or death regardless of tolerability, duration of study treatment, or initiation of subsequent anti-cancer therapy. Data from randomized participants who do not meet per-protocol criteria as defined below are excluded. The date of the event (event as defined in Table 10) is the date of disease assessment documenting recurrence of high-grade disease, progression of disease, persistence of CIS (applicable only to participants with CIS at randomization), or death, whichever occurs earlier. The date of persistence of CIS is the earliest date when persistence of CIS is observed, if CR is not observed after re-induction.

- Variable: EFS defined as the time from randomization until recurrence of high-grade disease, progression of disease, persistence of CIS, or death due to any cause, whichever occurs first.
- Censoring: see Table 11
- Population-level summary measure: hazard ratio for EFS excluding randomized participants who did not receive at least 1 dose of study drug, did not meet inclusion criteria 2 or 3, or met exclusion criteria 1 or 2.

### 2.3. Study Design

This is a phase 3, multinational, randomized, open-label, three parallel-arm study of PF-06801591, an anti-PD-1 Antibody, in combination with Bacillus Calmette-Guerin (BCG induction with or without BCG maintenance) versus BCG (induction and maintenance) in participants with high-risk, BCG naïve non-muscle invasive bladder cancer (Cohort A) or PF-06801591 as single agent in participants with BCG-unresponsive NMIBC (Cohorts B1 and B2).

In Cohort A, a total of approximately 999 participants (including a minimum of 250 participants with CIS) will be randomized in a 1:1:1 ratio to one of 3 treatment arms below.

- Arm A: PF-06801591 + BCG (induction and maintenance period)
- Arm B: PF-06801591 + BCG (induction period only)
- Arm C: BCG only (induction and maintenance period)

Randomization will be stratified by the presence of CIS (yes vs no) and geography (US vs Western Europe and Canada vs Rest of World [ROW]).

[figure not shown]
In Cohort B1, approximately 110 participants with BCG-unresponsive CIS (with or without concomitant recurrent Ta/T1 disease) will be enrolled.

In Cohort B2, approximately 50 participants with BCG-unresponsive recurrent high-grade Ta/T1 only will be enrolled.

Participants discontinued from Cohort A are not permitted to enroll into Cohort B1 or Cohort B2.

As of 31 August 2022, enrollment in Cohorts B1 and B2 was closed by the sponsor for business strategy reasons. This decision was not made due to any safety concerns, new emerging data, or regulatory interaction. Participants that have already been enrolled into Cohorts B1 and B2 may continue treatment and study procedures and assessments per the Cohorts B1 and B2 Schedule of Activities in protocol amendment 5.

[figure not shown]
**Figure 1. Study Design Schema (Cohort A)**

\* For participants with CIS at randomization

CIS: carcinoma in situ, BCG: Bacillus Calmette-Guerin; ROW: rest of world; US: United States

**Figure 2. Study Design Schema (Cohorts B1 and B2)**

\*See Section 4.1 for additional details

\*\*For participants in Cohort B1 with CIS at registration

CIS: carcinoma in situ

### 3. ENDPOINTS AND BASELINE VARIABLES: DEFINITIONS AND CONVENTIONS

#### 3.1. Primary Endpoint

##### Cohort A

- EFS for Arm A vs Arm C as assessed by the investigator

EFS is defined as time from randomization to the earliest of recurrence of high-grade disease, progression of disease, persistence of CIS, or death due to any cause.

##### Cohort B1

- CR as assessed by the BICR (in participants with CIS at baseline as assessed by the BICR)

CR is defined as histologic disappearance of malignancy on bladder biopsy with negative cytology and cystoscopy or negative cytology and positive cystoscopy with biopsy-proven low-grade Ta lesion or non-malignant tissue.

### Cohort B2

- EFS as assessed by the investigator

EFS is defined as time from date of initiation of study intervention (i.e. first dose) to the earliest of recurrence of high-grade disease, progression of disease, or death due to any cause.

## **3.2. Secondary Endpoints**

### **3.2.1. Safety endpoints**

- AEs as characterized by type, severity (as graded by NCI CTCAE v5.0), timing, seriousness, and relationship to study therapy.  
AEs will be graded by the investigator according to the CTCAE v5.0 and coded using the Medical Dictionary for Regulatory Activities (MedDRA).
- Laboratory abnormalities as characterized by type, severity (as graded by NCI CTCAE v5.0), and timing.

### **3.2.2. Efficacy endpoints**

#### Cohort A

- Key Secondary: EFS for Arm B vs Arm C as assessed by the investigator

EFS is defined as time from randomization to the earliest of recurrence of high-grade disease, progression of disease, persistence of CIS, or death due to any cause.

- Key Secondary: OS  
OS is defined as the time from the date of randomization to the date of death due to any cause.
- EFS as assessed by the BICR  
EFS is defined as time from randomization to the earliest of recurrence of high-grade disease, progression of disease, persistence of CIS, or death due to any cause.
- CR as assessed by the investigator (in participants with CIS at randomization)  
CR is defined as histologic disappearance of malignancy on bladder biopsy with negative cytology and cystoscopy or negative cytology and positive cystoscopy with biopsy-proven low-grade Ta lesion or non-malignant tissue
- DoCR for participants with CR as assessed by the investigator (in participants with CIS at randomization)

DoCR is defined as the time from the first documentation of CR to the date of an EFS event for participants with CR.

- Time to recurrence of low-grade disease as assessed by the investigator

Time to recurrence of low-grade disease is defined as the time from randomization to the date of first documentation of recurrence of low-grade disease.

- Time to cystectomy

Time to cystectomy is defined as time from randomization to cystectomy.

- DSS as assessed by the investigator

DSS is defined as the time from randomization to death resulting from bladder cancer, as assessed by the investigator.

#### Cohorts B1 and B2

- CR as assessed by the investigator (in participants with CIS at baseline; Cohort B1 only)

CR is defined as histologic disappearance of malignancy on bladder biopsy with negative cytology and cystoscopy or negative cytology and positive cystoscopy with biopsy-proven low-grade Ta lesion or non-malignant tissue.

- EFS as assessed by the investigator (Cohort B1 only)

EFS is defined as time from date of initiation of study intervention (i.e. first dose) to the earliest of recurrence of high-grade disease, progression of disease, persistence of CIS, or death due to any cause.

#### **3.2.3. Patient reported outcomes (Cohort A)**

- Health-related quality of life as measured by: 1) EORTC QLQ-C30, 2) EORTC QLQ-NMIBC24, 3) PTAB

The EORTC QLQ-C30 is a 30-question survey, which can be grouped into 5 functional domain subscales, including a physical functioning subscale, a role functioning subscale, an emotional functioning subscale, a cognitive functioning subscale and a social functioning subscale. Higher scores on the functional domains are indicative of higher levels of functioning. Oncology related symptoms assessed by the EORTC QLQ-C30 include fatigue (3 items), pain (2 items), nausea and vomiting (2 items), and dyspnea, insomnia, appetite loss, constipation, diarrhea, and financial impact (1 item each). Higher scores are reflective of a greater presence of symptoms.

The NMIBC24 has 24 items which can be grouped into 6 subscales: urinary symptoms (7 items), malaise (2 items), future worries (4 items), bloating/flatulence (2 items), sexual functioning (2 items), and male sexual issues (2 items). The NMIBC24 also assesses intravesical treatment, female sexual issues, sexual intimacy, risk of contaminating a partner, and sexual enjoyment (1 item each). Higher scores indicate greater impairment, with the exception of the sexual function and sexual enjoyment items, where higher scores indicate better function.

The PTAB questionnaire is a 2-item PRO designed to assess, from the participant perspective, any pain associated with the treatment administration and the burden of the amount of time required to complete the treatment administration procedures (1 item each).

### 3.2.4. Pharmacokinetic endpoints

- $C_{trough}$  of PF-06801591 when in combination with BCG (induction and maintenance or induction); Arms A and B only in Cohort A.

$C_{trough}$  will be reported after single dose and at steady state.

**Table 4. PK Parameters to be Determined for PF-06801591**

Parameter	Definition	Method of Determination
$C_{trough}$	Predose/trough concentration	Observed directly from data

### 3.2.5. Immunogenicity endpoints

- Anti-drug antibodies (ADAs); neutralizing antibodies (Nabs) of PF-06801591 when in combination with BCG (induction and maintenance or induction). Arms A and B only in Cohort A.

### 3.2.6. Biomarker endpoints

- Tumor sample biomarker status based on PD-L1 expression (high or low).

**Table 5. Biomarker Definition and Determination**

Parameter	Definition	Method of Determination
PD-L1 expression	The number of PD-L1 positive cells and/or qualitative assessment of PD-L1 staining on tumor and immune cells in regions of interest that are defined by tumor cell morphology.	Pathologist, assisted by image analysis

## 3.3. Tertiary/Exploratory Endpoints

The following endpoints apply to Cohort A.

- Health state utilities as measured by the EQ-5D-5L & VAS

The EQ-5D-5L is a 6-item patient-completed questionnaire designed to assess health status in terms of a single index value or utility score. There are 2 components, a Health State Profile which has individuals rate their level of problems (none, slight, moderate, severe, extreme/unable) in 5 areas (mobility, self-care, usual activities, pain/discomfort, and anxiety/depression), and a VAS in which participants rate their overall health status from 0 (worst imaginable) to 100 (best imaginable). Published weights are available that allow for the creation of a single summary score. Overall scores range from 0 to 1, with lower scores representing a higher level of dysfunction.

- Overall assessment of disease severity as measured by the PGIS

The PGIS is a single-item PRO designed to facilitate an anchor-based methodology for establishing meaningful within person change (MWPC) of other PRO-based endpoints such as the EORTC QLQ-C30 and NMIBC24. There are 4 response options, ranging from “none” to “severe”.

- Overall assessment of change as measured by the PGIC

The PGIC is a single-item PRO designed to assess the participant’s overall impression of the degree of change they have experienced since the start of study treatment. There are 5 response options, ranging from “much worse” to “much better”.

- Patient satisfaction as measured by the TSQ

The TSQ is a 3-item PRO designed to assess participant’s satisfaction with the study treatments. The TSQ assesses overall satisfaction with the study treatment, number of treatment administrations, and the form of treatment administration (injection into stomach and catheter into bladder) (1 item each).

- Peripheral blood and additional tumor tissue biomarkers consisting of the levels of cells, deoxyribonucleic acid (DNA), ribonucleic acid (RNA), or proteins that may be related to anti-tumor immune response or disease progression.

### **3.4. Baseline Variables**

#### **3.4.1. Study drug, study treatment and baseline definitions**

In this study, ‘**study drug**’ refers to PF-06801591 or BCG and ‘**study treatment**’ (or ‘**treatment arm**’ or ‘**cohort**’) refers to one of the following:

##### BCG Naïve Cohort (Cohort A)

- Arm A: PF-06801591 + BCG (induction and maintenance period)
- Arm B: PF-06801591 + BCG (induction period only)
- Arm C: BCG only (induction and maintenance period)

##### BCG-Unresponsive Cohorts

- Cohort B1: CIS with or without papillary disease: PF-06801591 only
- Cohort B2: Papillary disease only: PF-06801591 only

##### **Start and end dates of study treatment:**

For Arm A and Arm B in Cohort A:

The date/time of first dose of study treatment in a combination arm is the earliest date/time of the first non-zero dose date/time for any of the study drugs in the combination.

The date/time of last dose of study treatment in a combination arm is the latest date/time of the last non-zero dose date/time for any of the study drugs in the combination.

For Arm C (BCG only) in Cohort A and Cohorts B1 and B2 (PF-06801591 only):

The date/time of first dose of study treatment is the earliest date/time of non-zero dosing of the study drug.

The date/time of last dose of study treatment is the latest date/time of non-zero dosing of the study drug.

### **Definition of baseline:**

‘Start date’ will be defined as date of randomization for Cohort A and date of first dose for Cohorts B1 and B2.

#### Definition of baseline for efficacy and PRO analyses

The last assessment prior to ‘start date’ will serve as the baseline assessment for efficacy and PRO analyses. For Cohort A only, if such a value is missing (since per protocol for some PRO endpoints the first assessment is planned to occur prior to dosing on Cycle 1 Day 1), the last assessment prior to the date of first dose of study treatment will be used as the baseline assessment except for analyses of disease assessment data where the baseline assessment would be considered as missing.

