Coagulation	X							X	Not necessary to repeat on C1D1 if performed within 7 days prior to C1D1 as part of Screening. Laboratory tests may be performed up to 3 days prior to the scheduled clinic visit, so that results will be available for review before study treatment administration, including C1D1. See Section 8.2.7 for requirements on minimum labs to be reviewed prior to dosing.
Urinalysis	X	X				X		X	Collect sample before BCG administration. Not necessary to repeat on C1D1 if performed within 7 days prior to C1D1 as part of Screening. See Section 10.2 for the list of the tests.
Pregnancy Test	X	X				X		X	A negative highly sensitive test is required prior to study treatment dosing on Day 1 of all cycles. Results must be available for review prior to dosing. See Section 8.2.8 and Section 10.4 . Pregnancy testing after C1D1 per local guidelines.
FSH	X								For female postmenopausal participants under the age of 60 and not using hormonal contraception or HRT, a serum FSH test is required at screening only, to confirm postmenopausal status. FSH is not required for participants not meeting these criteria. See Section 10.2 and Section 10.4 .
Hepatitis B and C	X								HBV surface antigen and anti-HCV antibody tests. If HBV surface antigen or anti-HCV antibody test is positive, reflex testing must be carried out, as detailed in Table 5
ACTH & Thyroid Function Test	X	X				X		X	Not necessary to repeat on C1D1 if performed within 7 days prior to C1D1 as part of Screening.
Randomization		X							Participants will receive assigned treatment within 3 days after randomization.
BCG Administration (All Arms)		X	X	X	X	X	X		Follow calendar days for dosing, not the schedule cycles. See Section 6.1.2 for details. On days when BCG and PF-06801591 are both administered, BCG is administered first.
PF-06801591 Administration (Arms A & B)		X				X		X	Administer subcutaneously. See Section 6.1.2 .
Disease Assessments									
CT or MRI	X					As clinically indicated	CT/MRI/Urogram of the abdomen and pelvis/urinary tract. Imaging performed with contrast agents unless contraindicated for medical reasons. As clinically indicated to confirm and/or rule out distant metastasis. See Section 8.1.1.3 for additional details.		
Cystoscopy, with or without Biopsy	X								Cystoscopy is required during screening. Same equipment and methods by the same study staff should be used for the duration of the study whenever possible. See Section 8.1.1.1 .

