Visit Window (Days)	Screening	Induction Period							Notes
	D -28 to D -1	Cycle 1				Cycle 2		Cycle 3	
		D1 ±0	D8 ±3	D15 ±3	D22 ±3	D1 ±3	D8 ±3	D1 ±3	
Cytology	X								Urine cytology; ±7 days allowed for on-treatment assessment. Same equipment and methods by the same study staff should be used for the duration of the study whenever possible. See Section 8.1.1.2.
Patient Reported Outcomes (PROs)									
EORTC-QLQ-C30, EORTC NMIBC24	X	X				X		X	All PROs will be completed prior to clinical assessments and procedures and/treatment administration, with the exception of the PTAB, which will be completed immediately after treatment administration. Laboratory assessments may be done prior to PROs if laboratory assessments are done on a date prior to the rest of the study visit. PROs will be administered in following order: EORTC QLQ-C30, EORTC NMIBC24, EQ-5D-5L, PGIS, PGIC, TSQ, PTAB. See Section 8.1.2.
EQ-5D-5L		X				X		X	
PGIS	X	X				X		X	
PGIC						X		X	
TSQ						X			
PTAB		X				X			
Immunogenicity, Pharmacokinetic, Pharmacodynamic, Biomarker Analyses									
Immunogenicity		X				X			Collected pre-dose at each time point for Anti-PF-06801591 Antibody (ADA/NAb) measurement. See Section 8.8.3. Arms A and B only.
Pharmacokinetics		X				X			Collected pre-dose at each time point for PK analysis of PF-06801591. All efforts should be made to obtain PK samples within 2 hours prior to PF-06801591 dosing. See Section 8.5. Arms A and B only.
Tumor Tissue Sample from Most Recent TURBT	X								See Section 8.8.1.
Whole Blood Biomarkers	X	X				X			See Section 8.8.
Plasma and Serum Biomarker Sample	X	X				X			See Section 8.8.
Banked Biospecimen		X							See Section 8.7.2.

AE: adverse event, ACTH: adrenocorticotrophic hormone, ADA: anti-drug antibodies; BCG: *Bacillus Calmette Guérin*, BP: blood pressure; CT: computed tomography, ECG: electrocardiogram, ECOG PS: Eastern Cooperative Oncology Group Performance Status, EORTC-QLQ-C30: European Organisation for Research and Treatment of Cancer Quality of Life Questionnaire-30 (items), FSH: follicle-stimulating hormone, HRT: hormone replacement therapy, MRI: magnetic resonance imaging, NAb: neutralizing antibodies; NMIBC: non-muscle invasive bladder cancer, PGIC: Patient Global Impression of Change; PGIS: Patient Global Impression of Severity; PK: pharmacokinetics, PTAB: Patient Treatment Administration Burden; TSQ: Treatment Satisfaction Questionnaire; TURBT: transurethral resection of bladder tumor

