Cytology	X			X			X			X		X*	Urine cytology; ±7 days allowed for on-treatment assessment. Same equipment and methods by the same study staff should be used for the duration of the study whenever possible. See Section 8.1.1.2. *Completed every 12 weeks.
Patient Reported Outcomes (PROs)													
EORTC-QLQ-C30, EORTC NMIBC24,	X	X	X	X			X			X		X*	All PROs will be completed prior to clinical assessments and procedures and treatment administration, with the exception of the PTAB, which will be completed immediately after treatment administration. Laboratory assessments may be done prior to PROs if laboratory assessments are done on a date prior to the rest of the study visit. See
EQ-5D-5L	X	X	X	X			X			X		X*	
PGIS	X	X	X	X			X			X		X*	
PGIC	X	X	X	X			X			X		X*	
TSQ	X			X						X		X*	

Maintenance Period: Cycles 4 to 25 (Cycle = 4 Weeks) for participants without re-induction BCG Re-induction Period for Participants Who Receive BCG Re-induction: Cycles 4-6 ; Maintenance Period: Cycles 7 to 25													
	C4D1	C5D1	C6D1	C7D1	C8D1	C9D1	C10D1	C11D1	C12D1	C13D1	C14D1	C15D1 thru C25D1	Notes
Visit Window (Days)	±7	±7	±7	±7	±7	±7	±7	±7	±7	±7	±7	±7	
PTAB	X			X						X		X*	Section 8.1.2. PROs will be administered in the following order: EORTC QLQ-C30, EORTC NMIBC24, EQ-5D-5L, PGIS, PGIC, TSQ, PTAB. *Completed on Day 1 of Cycles 19 and 25.
Immunogenicity, Pharmacokinetic, and Pharmacodynamic Biospecimen													
Immunogenicity	X		X		X		X			X			Collected pre-dose at each time point for Anti-PF-06801591 Antibody (ADA/NAb) measurement. See Section 8.8.3. Arms A and B only.
Pharmacokinetics	X		X		X		X			X			Collected pre-dose at each time point for PK analysis of PF-06801591. All efforts should be made to obtain PK samples within 2 hours prior to PF-06801591 dosing. See Section 8.5. Arms A and B only.
Whole blood biomarkers	X		X		X		X			X			See Section 8.8.
Plasma and Serum Biomarker Sample	X		X		X		X			X			See Section 8.8.

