#### **6.3.1.6 Random Coefficient Models**

Random coefficient models will be carried out in Cohort A for the EORTC QLQ-C30 and NMIBC24 (all domains, subscales and symptoms), EQ-5D-5L (Index), and EQ-VAS using PROC MIXED. Outcomes are post-baseline scores and change scores and the predictors are the corresponding baseline PRO score, treatment, time (treated as a continuous variable), and treatment-by-time interaction. Intercept and time are considered as random effects particular to each participant. All available data for each participant prior to the end of therapy should be used in the analyses. All parameter estimates should be obtained using restricted

maximum likelihood. The unstructured covariance structure should be used to define covariance between random effects (using option “Type=UN” as a part of the RANDOM statement in PROC MIXED). For the degrees-of-freedom calculations the Kenward and Roger algorithm should be used (using option ddfm = kr”) as a part of the MODEL statement in PROC MIXED).

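### As written, the PRO model counts pre-dose Cycle 1 Day 1 QLQ-C30 and NMIBC24 scores as post-baseline outcomes, and the fallback baseline rule misses a same-day EQ-5D-5L

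*SAP*

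**What the plan says.** **Baseline rule (SAP 3.4.1).** PRO baseline is the last assessment before the start date, which "will be defined as date of randomization for Cohort A and date of first dose for Cohorts B1 and B2". If there is none, then for Cohort A "the last assessment prior to the date of first dose of study treatment will be used as the baseline assessment". The reason given for this fallback is "since per protocol for some PRO endpoints the first assessment is planned to occur prior to dosing on Cycle 1 Day 1".

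**Schedule (Protocol 1.3, Cohort A).** QLQ-C30 and NMIBC24 are collected at screening, within the 28 days before Day 1, and again at C1D1, C2D1 and C3D1. EQ-5D-5L has no screening assessment and starts at C1D1. Later visits for all three are Day 1 of Cycles 4, 5, 6, 7, 10 and 13, then "Completed on Day 1 of Cycles 19 and 25". On timing within a visit, "All PROs will be completed prior to clinical assessments and procedures and/treatment administration"; only PTAB is completed afterwards. On timing of the first dose, "Participants will receive assigned treatment within 3 days after randomization".

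**Model (SAP 6.3.1.6).** Random coefficient models are fitted for QLQ-C30, NMIBC24 and EQ-5D-5L (index and VAS). "Outcomes are post-baseline scores and change scores"; the predictors are the baseline score, treatment, continuous time and treatment-by-time. All available data before end of therapy are to be used. The SAP does not define post-baseline for PROs and does not mention C1D1 here.

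**The concern.** For QLQ-C30 and NMIBC24, the first sentence of the baseline rule settles the matter whenever a screening score exists. Baseline is screening, and the C1D1 score comes after it. Taking post-baseline in its ordinary sense, C1D1 is then an outcome record, although nobody has been treated when it is completed.

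The true arm difference attributable to treatment is zero at that record. Including it pulls the fitted difference towards zero at the start and can tilt the treatment-by-time term. Quality of life on these two instruments is a stated secondary objective, and this is the only model in the SAP that compares arms on PROs; the other PRO outputs are descriptive.

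The EQ-5D-5L issue is separate. A questionnaire completed on the dosing date is not before that date, so the fallback, read literally, does not reach the C1D1 record that it gives as its own reason. Without a baseline there is no change score and no value for the baseline predictor.

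**Working it through.** The plan gives no figure on this point to reproduce. The check applies the baseline rule to the schedule and then projects an assumed effect onto the planned model.

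**1. Which record is the baseline?** Let randomization be day 0 and first dose be day 0, 1, 2 or 3.

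| Instrument | Records available | Baseline as written |
|---|---|---|
| QLQ-C30, NMIBC24 | Screening and C1D1 | Screening, at every lag |
| EQ-5D-5L, completed on the dosing date | C1D1 only | None, at every lag |
| EQ-5D-5L, completed on day 0 and dosed on day 1, 2 or 3 | C1D1 only | The day 0 record |

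If the fallback accepts a pre-dose record on the dosing date, EQ-5D-5L has a baseline in every case. The QLQ-C30 and NMIBC24 result does not change, because the fallback applies only when the first value is missing.

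**2. Effect on the model.** Cycle k Day 1 is week 4(k − 1), so the scheduled records fall at weeks 0, 4, 8, 12, 16, 20, 24, 36, 48, 72 and 96. One of the 11 is pre-dose. Assume complete data and a true arm difference d(t) of 0 at week 0 and 5 points at every later visit. With complete, balanced visits and random intercept and slope on the same time terms, generalized least squares equals ordinary least squares, so the variance components do not matter.

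With C1D1 included:

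- n = 11, Σt = 336, Σt² = 19,456
- Sxx = 19,456 − 336²/11 = 9,192.7
- Sxy = 5 × 336 − 336 × 50/11 = 152.7
- slope = 152.7/9,192.7 = 0.0166 per week
- intercept = 50/11 − 0.0166 × 336/11 = 4.04
- fitted difference: 4.10 at week 4, 4.84 at week 48, 5.63 at week 96
- mean over the ten on-treatment visits (mean week 33.6) = 4.60

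With C1D1 excluded, the fit returns 5.0 at every visit and slope 0.

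For a participant set with visits only to week 24 (n = 7):

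- Sxx = 1,456 − 84²/7 = 448
- Sxy = 420 − 360 = 60
- slope = 60/448 = 0.134 per week
- intercept = 30/7 − 0.134 × 12 = 2.68
- fitted difference: 3.21 at week 4, 5.89 at week 24

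**3. Other effect shapes, same 11 visits.**

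- Difference growing linearly from zero at week 0: the week 0 record lies on the true line, so intercept and slope are exact with C1D1 included.
- Difference rising linearly to 5 over 12 weeks, then flat: slope 0.030 per week with C1D1 and 0.017 without. A straight line in time does not fit this shape either way, and including C1D1 makes the slope steeper.

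**4. Same-day provisions elsewhere in SAP 3.4.1.** When the time is missing, the safety, immunogenicity and biomarker baselines each presume that a planned pre-dose assessment on the first dosing day was made before treatment. The PRO definition has no such provision.

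**The case against.** **A pre-randomization baseline is a legitimate choice.** The trial is open-label. A score taken before randomization cannot be coloured by knowing the arm, whereas a C1D1 score might be. This stands: the screening baseline need not be replaced. It does not explain why a pre-dose record should serve as an outcome.

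**The intent for EQ-5D-5L is plain.** The fallback's parenthesis shows that the C1D1 questionnaire was meant to count, and a programmer following intent would include it. This stands. A reader might infer that most participants will have no EQ-5D-5L baseline. The documents do not support that: they give no count of questionnaires completed on the dosing date, dosing may follow randomization by up to three days, and the literal reading runs against the rule's own stated purpose.

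**The distortion depends on the assumed effect.** This also stands. A reader might infer that including C1D1 always creates a false treatment-by-time slope. It does so for an immediate, constant effect, but not for one growing linearly from zero. Under the constant effect the average attenuation is modest, 4.60 against 5.0. Agreement across variance settings is no evidence of robustness, since with complete data the result cannot depend on them.

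**Reach is limited.** No PRO is in the alpha-controlled testing sequence.

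**Conclusion.** The point holds for QLQ-C30 and NMIBC24. Following SAP 3.4.1 and 6.3.1.6 as written puts a pre-treatment record into the only between-arm PRO model, and no stated intent excludes it. This rests on two conditions: a screening score exists, and post-baseline has its ordinary meaning.

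The size is conditional. For an immediate, constant 5-point difference with complete data, the fitted difference is about 4.1 at week 4 and 5.6 at week 96, or 3.2 and 5.9 at weeks 4 and 24 if visits stop at week 24. The documents do not say which effect shape to expect, so these figures are illustrative.

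The EQ-5D-5L part is a wording contradiction in an exploratory endpoint, with the number affected not stated. EFS and OS are unaffected.

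**What to change.** 1. In SAP 6.3.1.6, state that any questionnaire completed before the first dose is excluded from the outcomes, for scores and change scores alike. Keep the pre-randomization score as the covariate where it exists. This alone removes the distortion for QLQ-C30 and NMIBC24.
2. In the SAP 3.4.1 fallback, replace the reference to the date of first dose with the last assessment before the first dose, and treat a C1D1 questionnaire on the dosing date as pre-dose. This brings it into line with the safety, immunogenicity and biomarker definitions in the same section.

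The cost is SAP wording only; all the data are already scheduled for collection. Moving the QLQ-C30 and NMIBC24 baseline to C1D1 is not needed and would be a trade-off in an open-label trial.
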